### **13.6 Inclusion of Women and Minorities**

In conformance with the National Institute of Health Revitalization Act of 1993 with regard to inclusion of women and minorities in clinical research, we have also considered the possible interaction between race and treatments. Some investigators have shown gender to be a prognostic factor in NSCLC. However, the RTOG did not show this to be the case in a recent analysis. Furthermore, an analysis of race did not indicate an association with outcome. The projected gender and minority accruals are provided in Table 13.2 below.

**Table 13.2: Projected Distribution of Gender and Minorities**

	Gender		
Ethnic Category	Females	Males	Total
Hispanic or Latino	2	3	5
Not Hispanic or Latino	38	51	89
Ethnic Category: Total of all subjects	40	54	94
	Gender		
Racial Category	Females	Males	Total
American Indian or Alaskan Native	1	3	4
Asian	1	3	4
Black or African American	3	2	5
Native Hawaiian or other Pacific Islander	0	0	0
White	35	46	81
Racial Category: Total of all subjects	40	54	94

**APPENDIX II: STUDY PARAMETER TABLE (\*See Sections 11.2 for details) [8/20/10]**

Assessments	Pre-Treatment				During Treatment	Follow Up	
	Within 12 wks prior to registration	Within 8 wks prior to registration	Within 4 wks prior to registration	Within 2 wks prior to treatment		6 wks from start of SBRT	q3 mos. from the start of SBRT for years 1-2 then q6 mos. for years 3 & 4, then annually
History/physical			X		X	X	X
Weight			Within 4 wks prior to tx				X
Chest x-ray				X		X	At 9, 15, and 21 months
CT scan with contrast		X					At 6, 12, 18, and 24 months
PET with FDG		X					Recommended If suspicion of tumor recurrence
Performance status			X		X		X
Thoracic surgeon eval	X						
CBC w/ diff & ANC		Within 8 wks prior to tx					
Spirometry, lung volumes, diffusion capacity, arterial blood gases	Within 12 wks prior to tx						PFTs and blood gases at 6 and 12 months
Serum/urine pregnancy test (if applicable)				Within 72 hrs. prior to registration			
Tumor response eval							At 6, 12, 18, and 24 months
Charlson Index & hospitalization history	Within 12 wks prior to tx						
Tissue, urine, blood for banking & trans. research				X*	X*	X	
Adverse event eval**					X	X	X
T5 Form							Fax Daily Treatment Record (T5) to RTOG HQ on patient's last day of treatment

\*See Sections 11.2 for details

\*\*And as needed based on reporting requirements: See Sections 4.1.5, 6.10, and 12.1.

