#### **11.3.2 *Baseline Documentation of "Target" and "Non-Target Lesions"***

Patients enrolled to this protocol should have clinical stage I (T1 or T2, N0, M0) or clinical stage II (T3 chest wall primaries only, N0, M0) NSCLC. At time of treatment, they should have only one site of gross disease in the lung, with no metastases. The primary lung tumor should be identified as the **target lesion** and recorded and measured at baseline and with each follow-up imaging evaluation.

The longest diameter (LD) for the target lesion will be calculated **from the treatment planning CT scan** using pulmonary windowing and reported as the baseline LD. The baseline LD will be used as a reference by which to characterize the objective tumor. For follow-up assessment, diagnostic CT scans performed using a 5 mm contiguous reconstruction algorithm using pulmonary windowing taken as part of scheduled protocol follow-up are preferred as the method of evaluation for response. When CT scans are not available, chest x-ray determination will be allowed as long as the target lesion is clearly visible. Changes in serum tumor markers will not be allowed for assessment of either local tumor progression or metastatic progression.

Local treatment effects in the vicinity of the tumor target may make determination of tumor dimensions difficult. For example, bronchial or bronchiolar damage may cause patchy consolidation around the tumor that over time may coalesce with the residual tumor. In cases

in which it is indeterminate whether consolidation represents residual tumor or treatment effect, it should be assumed that abnormalities are residual tumor

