### 11.3.3 Response Criteria (8/20/10)

Evaluation of Target and Involved Lobe Lesions	
Complete Response (CR)	Disappearance of the target lesion; ideally, this determination will be made based on CT image evaluation.
Partial Response (PR)	At least a 30% decrease in the LD of the target lesion, taking as reference the baseline LD; ideally, this determination will be made based on CT image evaluation.
Stable Disease (SD)	Neither sufficient shrinkage to qualify for CR/PR above nor sufficient increase to qualify for LE below, taking as reference the smallest LD since the treatment started
Local Enlargement (LE)	At least a 20% increase in the LD of target lesion, taking as reference the smallest LD recorded since the treatment started; Ideally, this determination will be made based on CT image evaluation.
Primary Tumor Failure (PTF)	Refers to the primary treated tumor after protocol therapy and corresponds to meeting both of the following two criteria: 1) Increase in tumor dimension of 20% as defined above for local enlargement (LE); 2) The measurable tumor with criteria meeting LE should be avid on Positron Emission Tomography (PET) imaging with uptake of a similar intensity as the pretreatment staging PET, OR the measurable tumor should be biopsied confirming viable carcinoma. For outcome analysis, Marginal Failures (MF; see below) will also be counted as PTF; however, they should be distinguished specifically as MF, not PTF, on all report forms. The EORTC criteria for post-treatment PET evaluation will be used as a basis for evaluation in cases more difficult to assign as to whether the uptake is pathological for cancer recurrence vs. inflammation. 
Marginal Failure (MF)	Refers to the appearance after protocol therapy of a measurable tumor appearing since treatment within 1.0 cm of the treated PTV (see Section 6.4) and meeting the following two criteria: 1) Enlarging tumor dimensions corresponding to a 20% increase in the longest diameter compared to initial appearance on imaging evaluation. Ideally, this determination will be made based on CT image evaluation; 2) The measurable tumor within 1.0 cm of the treated PTV should be avid on Positron Emission Tomography (PET) imaging with uptake of a similar intensity as the pre-treatment staging PET, OR the measurable tumor should be biopsied confirming viable carcinoma.
Primary Tumor Control (PTC)	The absence of Primary Tumor Failure.

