**13.5.1.2** 2-year Primary Tumor Control Rate at MTD (8/20/10)

Primary tumor control is the absence of local progression (defined as local enlargement confirmed by PET or biopsy which occurs within 2 years from the start of treatment). Marginal failures, which are mentioned in Section 11.3.3, will be considered events for local progression. Distant metastases from the index lung cancer or a second primary tumor are not considered local progression. Patients who die with lung cancer but no documented local progression will be considered non-failures and will be censored on the day of their death. Patients who die without progressive lung disease and have no documented local progression will be considered non-failures and will be censored on the day of their death. Cumulative incidence method will be used to estimate the 2-year primary tumor control rate at the MTD of SBRT. Using this confidence interval, the null hypothesis that the probability of 2-year primary tumor control at the selected target dose (MTD) is 0.7 or less will be tested. Ninety percent confidence interval for the probability of response will be constructed by bootstrapping.

**13.5.2** Analysis of Secondary Survival Endpoints

**13.5.2.1** Progression-Free Survival and Overall Survival (8/20/10)

The same patients used for DLT analysis will be used in these analyses, which will be performed after they have been potentially followed for 2 years. The failure event for progression-free survival (PFS) is defined as the first occurrence of local and/or regional disease progression, distant metastases, second primary tumor, or death due to any cause. Time to PFS is measured from the date of randomization to the date of the failure event for PFS. Overall survival (OS) time is measured from the date of randomization to the date of death due to any cause.

Kaplan-Meier estimation will be used to calculate OS and PFS rate at each radiation dose level. Cox proportional hazards regression will be used to characterize PFS and OS as a function of dose. As in the analysis of 2-year primary tumor control, possible confounding baseline demographic or clinical variables will be included in the regression model if there is evidence of significant imbalance between doses.

**13.5.2.2** Local Progression, Regional Failure, and Distant Metastases

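### Primary tumor failure needs PET or biopsy confirmation that the schedule only recommends, so a recurrence that enlarges but is never tested counts as controlled in the phase II test against 0.70

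*Protocol*

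**What the plan says.** - **Event definition (Section 11.3.3).** Primary tumor failure "corresponds to meeting both of the following two criteria". The first criterion is a 20% increase in the longest diameter (local enlargement, LE). The second is PET avidity with "uptake of a similar intensity as the pretreatment staging PET, OR the measurable tumor should be biopsied confirming viable carcinoma". Marginal failure also pairs a size criterion with PET or biopsy, and it counts as primary tumor failure in the outcome analysis.
- **Control (Section 11.3.3).** Primary tumor control is "The absence of Primary Tumor Failure".
- **Analysis (Section 13.5.1.2).** "Primary tumor control is the absence of local progression (defined as local enlargement confirmed by PET or biopsy", within 2 years of the start of treatment. Patients who die without documented local progression are non-failures, censored at death. The null hypothesis is that 2-year control at the MTD is 0.7 or less.
- **Schedule (Appendix II).** CT and tumor response evaluation fall "At 6, 12, 18, and 24 months". Follow-up PET is "Recommended If suspicion of tumor recurrence". There is no biopsy row.
- **Reason for confirmation (Section 6.9.3).** Bronchial injury can collapse lung next to the tumor, and collapsed lung looks like tumor on imaging. Investigators are sent to the strict Section 11 criteria so that this is not miscalled as progression.

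The protocol neither obliges PET or biopsy once LE is met nor says how LE without confirmation is analysed.

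**The concern.** The schedule looks routinely for the first half of the event and leaves the second half optional. Because control is the default state, an enlarging lesion that nobody tests is scored exactly like one that was tested and found negative. If the patient then dies, the censoring rule leaves that status in place.

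This affects the phase II primary endpoint and its hypothesis test. The same definition also serves the secondary endpoint of local progression (Section 13.5.2.2). For metastatic dissemination, by contrast, Section 11.3.3 encourages confirmation without requiring it, so a missing test there does not remove the event.

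An unconfirmed true recurrence moves the estimate in one direction only, towards rejecting the 0.70 null. Sites that test less would tend to show better control.

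**Working it through.** **1. Inputs.** Null control rate 0.70 (Section 13.5.1.2). One-sided level 0.05 (Section 13.2.3). The number at the MTD is not fixed in advance. Section 13.2.3 expects 7-14 patients at each of Levels 5-8 when the design assumptions hold. If nobody is treated below Level 5, that leaves 75 - 4×14 = 19 to 75 - 4×7 = 47 of the 75 evaluable patients at Level 9. I use n = 30 as a working value within that range. The share *u* of true failures never confirmed within 2 years is not given anywhere, so 10%, 20% and 30% are assumptions.

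**2. Apparent control rate.** With true control 0.70, apparent control = 1 - 0.30 × (1 - u):
- u = 10%: 1 - 0.27 = 0.73
- u = 20%: 1 - 0.24 = 0.76
- u = 30%: 1 - 0.21 = 0.79

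Each unconfirmed true failure adds 1/30 = 3.3 points at n = 30.

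**3. Chance of rejecting the null when true control is 0.70.** At n = 30 the smallest count *x* with P(X ≥ x | 0.70) ≤ 0.05 is 26, since P(X ≥ 26) = 3.0% and P(X ≥ 25) = 7.7%. Putting the apparent rates into P(X ≥ x), for n = 30 and for n = 19, 25, 30, 33, 40 and 47:

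| Unconfirmed share | Apparent rate | Rejection, n = 30 | Range over n |
|---|---|---|---|
| 0 | 0.70 | 3.0% | 2.4-4.6% |
| 10% | 0.73 | 6.3% | 5.7-8.6% |
| 20% | 0.76 | 12.1% | 11.7-17.2% |
| 30% | 0.79 | 21.5% | 19.9-32.2% |

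**4. Check against the planned design.** A simulation of the dose-finding rules (600 trials, 75 patients, the model and prior of Section 13.4.1, the design toxicity scenario), followed by logistic regression of control on dose as in Section 13.2.3, gave power 0.775 at a Level 9 control rate of 0.89 and 0.809 at 0.90. The protocol states more than 80% from 0.89. The agreement is close, and the protocol's simulation details are not given in full, so I make nothing of the gap. In the same simulation, with Level 9 control at 0.70, rejection was 0.038 with full confirmation and 0.078, 0.161 and 0.285 at u = 10%, 20% and 30%.

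**5. Cost of going too far the other way.** Suppose true control is 0.89 and 5 points of treatment-effect enlargement (assumed) go untested. If all of it counted as failure in the main test, apparent control would be 0.84. At n = 30, P(X ≥ 26) falls from 77% to 46%. At n = 40 (critical count 34) it falls from 86% to 54%.

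**The case against.** The strongest reply is that confirmation is deliberate. Section 6.9.3 explains why size alone misleads in central tumors, so untested enlargement may well be treatment effect. This stands. Such enlargement is rightly not a failure, adds no bias, and should not be turned into failure in the main test; step 5 shows what that could cost.

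A reader might also infer that the plan contradicts Section 11.3.2, which says of indeterminate consolidation that "it should be assumed that abnormalities are residual tumor". The text does not support this. That rule concerns how the lesion is measured, so it feeds the size criterion. It does not waive confirmation. If anything, it produces more LE that is not recurrence.

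Non-confirmation may also be rare. Every patient had pathologic proof and an FDG PET at entry, LE is itself grounds for suspicion, and a growing lesion seen early gets further chances at later visits. This is fair, and it is why the size stays unknown. PET is also not the only route, since biopsy serves equally, but neither is required. Finally, the planned analysis is a cumulative incidence estimate with a bootstrapped 90% interval, so the exact binomial figures are only a guide to scale.

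Handling of missing confirmation could be left to a statistical analysis plan. Such a plan could add a counting rule, but it could not supply a PET that was never done. The mismatch lies between the protocol's own endpoint definition and its own schedule.

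**Conclusion.** The point holds in a limited form. The endpoint needs a test that the schedule does not secure, and a true recurrence left untested is counted as controlled. The direction follows from the stated rules; the size does not. Under the assumed shares, about 10% unconfirmed true failures is enough to take the false-positive rate above the nominal 5%, and 30% takes it to roughly 20-32% by exact binomial over the plausible range of n.

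It would go too far to say that every unconfirmed LE inflates control, or that the control rate will in fact be inflated. Only true recurrences that are never confirmed contribute, and the protocol gives no rate for these.

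**What to change.** 1. **Appendix II.** Align the PET entry with the endpoint definition: PET confirmation is obtained once LE, or the marginal-failure size criterion, is recorded, unless a biopsy is done.
2. **Sections 11.3.3 and 13.5.1.2.** Keep confirmed failure as the primary definition.
3. **Section 13.5.1.2.** Report the number of patients at the MTD with unconfirmed LE. Repeat the 0.70 test with them counted as failures on the date of that CT, as a bounding sensitivity analysis. If every LE is tested, the two results coincide.

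The cost is small. A few PETs that are already recommended become expected, and there is one extra estimate, which may be less favourable than the main one.

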**APPENDIX III (2/16/10)**

**ZUBROD PERFORMANCE SCALE**

- 0 Fully active, able to carry on all predisease activities without restriction**
- 1 Restricted in physically strenuous activity but ambulatory and able to carry work of a light or sedentary nature. For example, light housework, office work**
- 2 Ambulatory and capable of all self-care but unable to carry out any work activities. Up and about more than 50% of waking hours**
- 3 Capable of only limited self-care, confined to bed or chair 50% or more of waking hours**
- 4 Completely disabled. Cannot carry on self-care. Totally confined to bed or**
- 5 Death**

## APPENDIX IV

### AJCC Staging Lung, 6th Edition, 2002

#### Primary Tumor (T)

- TX** Primary tumor cannot be assessed, or tumor proven by the presence of malignant cells in sputum or bronchial washings but not visualized by imaging or bronchoscopy
- T0** No evidence of primary tumor
- Tis** Carcinoma *in situ*
- T1** Tumor 3 cm or less in greatest dimension, surrounded by lung or visceral pleura, without bronchoscopic evidence of invasion more proximal than the lobar bronchus,\* (i.e., not in the main bronchus)
- T2** Tumor with any of the following features of size or extent: More than 3 cm in greatest dimension; Involves main bronchus, 2 cm or more distal to the carina; Invades the visceral pleura; associated with atelectasis or obstructive pneumonitis that extends to the hilar region but does not involve the entire lung
- T3** Tumor of any size that directly invades any of the following: chest wall (including superior sulcus tumors), diaphragm, mediastinal pleura, parietal pericardium; or tumor in the main bronchus less than 2 cm distal to the carina, but without involvement of the carina; or associated atelectasis or obstructive pneumonitis of the entire lung
- T4** Tumor of any size that invades any of the following: mediastinum, heart, great vessels, trachea, esophagus, vertebral body, carina; or separate tumor nodules in the same lobe; or tumor with a malignant pleural effusion\*\*

**\*Note:** The uncommon superficial tumor of any size with its invasive component limited to the bronchial wall, which may extend proximal to the main bronchus, is also classified T1.

**\*\*Note:** Most pleural effusions associated with lung cancer are due to tumor. However, there are a few patients in whom multiple cytopathologic examinations of pleural fluid are negative for tumor. In these cases, fluid is non-bloody and is not an exudate. Such patients may be further evaluated by videothoracoscopy (VATS) and direct pleural biopsies. When these elements and clinical judgment dictate that the effusion is not related to the tumor, the effusion should be excluded as a staging element and the patient should be staged T1, T2, or T3.

#### Regional Lymph Nodes (N)

- NX** Regional lymph nodes cannot be assessed.
- N0** No regional lymph nodes metastasis
- N1** Metastasis to ipsilateral peribronchial and/or ipsilateral hilar lymph nodes, and intrapulmonary nodes including involvement by direct extension of the primary tumor
- N2** Metastasis to ipsilateral mediastinal and/or subcarinal lymph node(s)
- N3** Metastasis to contralateral mediastinal, contralateral hilar, ipsilateral or contralateral scalene, or supraclavicular lymph node(s)

#### Distant Metastasis (M)

- MX** Distant metastasis cannot be assessed
- M0** No distant metastasis
- M1** Distant metastasis present

**Note:** M1 includes separate tumor nodule(s) in a different lobe (ipsilateral or contralateral)

**APPENDIX IV (Continued)  
AJCC Staging**

**STAGE GROUPING**

Occult Carcinoma	TX	N0	M0
Stage 0	Tis	N0	M0
Stage IA	T1	N0	M0
Stage IB	T2	N0	M0
Stage IIA	T1	N1	M0
Stage IIB	T2	N1	M0
	T3	N0	M0
Stage IIIA	T1	N2	M0
	T2	N2	M0
	T3	N1	M0
	T3	N2	M0
Stage IIIB	Any T	N3	M0
	T4	Any N	M0
Stage IV	Any T	Any N	M1

## APPENDIX V

### Comorbidity Scoring

#### Instructions for completing the CHARLSON COMORBIDITY INDEX (CCI):

1. Complete all patient/institution information or affix RTOG patient-specific label.
2. Follow the “Rules for Completing The Charlson Comorbidity Index” in this appendix.
3. Complete The Charlson Comorbidity Index” by noting “yes” or “no” for each disease.

#### Instructions for completing THE COMORBIDITY RECORDING SHEET:

1. Complete all patient/institution information or affix RTOG patient-specific label.
2. Extract all comorbidity elements you can identify and note them on the Recording Sheet. Place the elements in the most appropriate category. Be comprehensive. The rater ([name]) will determine the relevant diseases and modify the category if needed.
3. Include past surgeries, diseases, smoking history, and functional problems, such as incontinence or constipation.
4. For each condition include:
  - When (e.g., 6 months ago, 5 years ago, etc.);
  - Current symptoms;
  - Related treatment (e.g., surgery, stent placement, hearing aides, glasses, etc.);
  - Related laboratory values (e.g., CR, bilirubin);
  - Medications (scheduled/prn).
5. If a functional problem appears to be related to tumor or treatment, place **TR** after the diagnosis.
6. Specify as much as possible the dose/frequency of medications; the rater may use this information to rate the severity of a disease.
7. Leave the scoring column blank.

Contact [name]. at [contact] or [[contact]](mailto:[contact]) if you have questions.

The Recording Sheet and CCI must include the RTOG study number and case number; institution name and number; name of person completing the form; phone number of that person; and date of completion. The patient-specific label may be used; however, all pages must have a label affixed. **Comorbidity data will be submitted to RTOG Headquarters at the same time point as the initial assessment data (see Section 12.1).**

## APPENDIX V (Continued)

### Rules for Completing the Charlson Comorbidity Index (CCI)

(Charlson et al. *J Chron Dis.* 40:373-383, 1987) Adaptation: Do not count non-melanotic skin cancers or in situ cervical carcinoma.

Myocardial infarct	Hx of medically documented myocardial infarction
Congestive heart failure	Symptomatic CHF w/ response to specific treatment
Peripheral vascular disease	Intermittent claudication, periph. arterial bypass for insufficiency, gangrene, acute arterial insufficiency, untreated aneurysm (>=6cm)
Cerebrovascular disease (except hemiplegia)	Hx of TIA, or CVA with no or minor sequelae
Dementia	chronic cognitive deficit
Chronic pulmonary disease	symptomatic dyspnea due to chronic respiratory conditions (including asthma)
Connective tissue disease	SLE, polymyositis, mixed CTD, polymyalgia rheumatica, moderate to severe RA
Ulcer disease	Patients who have required treatment for PUD
Mild liver disease	cirrhosis without PHT, chronic hepatitis
Diabetes (without complications)	diabetes with medication
Diabetes with end organ damage	retinopathy, neuropathy, nephropathy
Hemiplegia (or paraplegia)	hemiplegia or paraplegia
Moderate or severe renal disease	Creatinine >3mg% (265 umol/l), dialysis, transplantation, uremic syndrome
2nd Solid tumor (non metastatic)	Initially treated in the last 5 years exclude non-melanomatous skin cancers and in situ cervical carcinoma
Leukemia	CML, CLL, AML, ALL, PV
Lymphoma, MM...	NHL, Hodgkin's, Waldenström, multiple myeloma
Moderate or severe liver disease	cirrhosis with PHT +/- variceal bleeding
2nd Metastatic solid tumor	self-explaining
AIDS	AIDS and AIDS-related complex Suggested: as defined in latest definition

